17.1 Sample size calculation

The sample size calculation has been determined taking the small patient population into account, while also aiming for an acceptably narrow 95% confidence interval for the ABR.

Sufficient inference on bleeding episodes for the primary CPoC criterion is judged to be accommodated by 30 patients.

It is expected that the treatment duration of the main part allowing for escalation time for some patients is on average 6 months in the below calculations.

When evaluating the power of the negative binomial analysis referred above, an annual bleeding rate of 4 is assumed for the end dose concizumab regimen, respectively in combination with an over-dispersion of 6. The power for concluding a bleeding rate lower than 12 then becomes approximately 95%. The power under varying values of true ABR and over-dispersion for the primary CPoC criterion are shown below in [Table 17-1](#).

Protocol
 Trial ID:NN7415-4255
 UTN:U1111-1179-3872
 EudraCT no.:2016-000614-29

~~CONFIDENTIAL~~

Date: 28 August 2018
 Version: 5.0
 Status: Final
 Page: 104 of 127

Novo Nordisk

Table 17–1 Power in comparison between concizumab prophylaxis treatment and an ABR threshold of 12 under different assumptions of ABR and over-dispersion.

Power	Over-dispersion		
	5	6	7
4	99%	95%	92%
5	95%	90%	86%
6	87%	81%	72%

For the secondary CPoC criterion that includes data prior to potential dose escalation, it is expected that the treatment duration of the main part is on average 8 months with an average ABR of 5.4 for the concizumab treated patients. This yields a marginal power of approximately 87% for the secondary CPoC criterion.

In prior Novo Nordisk trials conducted in haemophilia patients, the typical 1-year over-dispersion for non-inhibitor patients on prophylaxis with FVIII or FIX has been in the range 4-8, implying 24 weeks over-dispersion of 3-5 (e.g. in NN7008-3543, NN7088-3859 and NN7999-3747). On that background, an over-dispersion of 6 over the 24 weeks in the main part of the current trial is deemed realistic.

17.2 Definition of analysis sets

All dosed patients will be included in the Full Analysis Set (FAS) as well as in the Safety Analysis Set (SAS).

17.3 Primary endpoint

The primary endpoint is the number of bleeding episodes during at least 24 weeks from treatment onset. All treated bleeding episodes will be considered for this endpoint, including bleeding episodes recorded as post-surgical or caused by surgery or other medical for dental procedures.

The primary endpoint will be estimated using negative binomial regression with log of exposure time (the included observational period of the main part) as offset, providing an actual estimate of the ABR as well as a corresponding 95% confidence interval. The offset for first CPoC criterion is the log of the individual exposure time at the last dose level reached at the time of analysis excluding the 2 weeks run-in period for subjects on 0.15 mg/kg. The offset for the second criterion is the log of the individual exposure time in the main part.

This analysis has the underlying assumption that the missing data mechanism is “missing at random”, i.e. MAR. Under this assumption, the statistical behaviour of the missing data (given the observed responses and the mean value structure) is assumed to be the same as for the observed data. The endpoint will be estimated based on the full analysis set (FAS) and only data collected

Protocol
 Trial ID:NN7415-4255
 UTN:U1111-1179-3872
 EudraCT no.:2016-000614-29

~~CONFIDENTIAL~~

Date: 28 August 2018
 Version: 5.0
 Status: Final
 Page: 105 of 127

Novo Nordisk

prior to discontinuation of trial product or initiation of alternative treatment options will be used to draw inference.

17.4 Sensitivity analyses

To evaluate the robustness of the MAR assumption implied in the primary analysis, a modified tipping point analysis will be performed where patients having discontinued before finalization of the main part are assumed to have a worse outcome compared to what was observed during the main part of the trial. This will be done by adding a value Δ_i to the observed bleeding episodes in the main part of the trial before analysing the data. The offset is maintained as being the exposure during the main phase since it is not possible to identify the amount of missing observation time. The degree of worsening, Δ_i , will gradually be increased to evaluate at which point the upper 95% confidence limit of the prophylactic concizumab ABR is no longer below a threshold of 12. The results of the primary analysis will be considered robust if the tipping point is above what is considered clinical plausible.

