After trial completion, Novo Nordisk will supply each trial site with long-life CDs or other relevant electronic archiving containing the electronic Investigator Trial Master File (eITMF) for each trial site. These CDs or other relevant electronic archiving will contain site-specific trial documentation as well as trial specific news and other relevant trial information, including audit trail on documents and site staff users. The GHN Portal software and hardware implementation are compliant with the requirements of U.S. Food and Drug Administration (FDA) 21 CFR Part 11 and ICH E6 (EU directive for personal data protection)^{1, 29}.

Novo Nordisk will provide electronic tablets for reporting of all PROs questionnaires described in section [8.6.1](#) and in [Appendix 1](#). In case the electronic tablet is revoked the questionnaires will be available in paper.

Protocol
 Trial ID:NN7415-4255
 UTN:U1111-1179-3872
 EudraCT no.:2016-000614-29

~~CONFIDENTIAL~~

Date:	28 August 2018	Novo Nordisk
Version:	5.0	
Status:	Final	
Page:	102 of 127	

The eDiary software and hardware implementation are compliant with the requirements of FDA 21 CFR Part 11 and ICH E6 (EU directive for personal data protection)^{1, 29}. After trial completion, each trial site will be supplied with long-life CDs. These CDs will contain site-specific patient records including the patient's eDiaries and ePROs as PROs are handled separately from eDiary and audit trail including any data additions and corrections made on each form. The eDiary vendor will furthermore retain and securely store copies of all archived documents and data for 15 years or as required by local data retention laws for trial data

17 Statistical considerations

All endpoints referring to a time frame of at least 24 weeks will be evaluated in the main part of the trial, defined to end when the last patient have completed a minimum of 24 weeks of dosing or at LPFT (visit 2)+24 weeks if the last patient has withdrawn before visit 9. Please refer to [Figure 17-1](#) for further information. All available data up to the time point where the last patient ends 24 weeks of treatment or has withdrawn will in such case be used in the analysis of the main part.

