The referred comparisons will be made using a negative binomial model with log of *exposure time in main phase* as offset. For each criterion, evidence of effect will be concluded if the 95% confidence interval of the estimated ABR is below 12.

The value of 12 bleeds per year reflects conservatively a 50% reduction from the bleeding rate during on-demand treatment, which in previous trials typically has been reported to be above 30 bleeds per year³⁰⁻³². A confidence limit lower than 12 will also to a certain extent substantiate that the prophylactic efficacy of concizumab may be similar to that of FVIII replacement therapy where an estimated mean of 6.5 bleeds per year was observed³³.

Clinical arguments for the hierarchical test approach

Concizumab exhibits non-linear PK due to target mediated drug disposition and it is expected that the dose response curve of the ABR is rather steep. This implies that patients that are on a dose which is not efficacious are likely to bleed as patients that are not treated at all. The subset of data collected from the last dose clinically deemed as efficacious would reflect the efficacy of concizumab in the given patient.

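### The tipping-point analysis adds bleeds but no time for discontinued patients, calling the missing time unidentifiable; the common cut-off makes it known for criterion 2, and usable under one assumption for criterion 1

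*Protocol*

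**What the plan says.** All references are to protocol version 5.0.

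- **Section 17.4.** Patients who discontinue before the main part is over have Δ_i added to their bleed count, and Δ_i is raised until the upper confidence limit is no longer below 12. Exposure stays as observed: "The offset is maintained as being the exposure during the main phase since it is not possible to identify the amount of missing observation time". A result counts as robust if the tipping point lies beyond what is clinically plausible.
- **Section 17, opening paragraph.** The main part is "defined to end when the last patient have completed a minimum of 24 weeks of dosing or at LPFT (visit 2)+24 weeks", the latter applying if the last patient has withdrawn. Section 7 (primary completion date) likewise fixes the date when the last patient leaves early.
- **Section 17.3.** Only data from before the trial product is stopped or an alternative treatment is started are used. The offset for criterion 1 is time at the last dose level reached, without the two-week run-in for patients on 0.15 mg/kg. The offset for criterion 2 is time in the main part.
- **Section 17, clinical proof of concept.** For each criterion, "evidence of effect will be concluded if the 95% confidence interval of the estimated ABR is below 12".

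**The concern.** The reason given for leaving the offset alone conflicts with the protocol's own definition of the main part. The choice also matters. A negative binomial model with a log-exposure offset reads bleeds per unit of time. If bleeds assumed to happen after discontinuation are placed on the few weeks before it, the model sees a very high rate in those patients, and both the estimate and the fitted dispersion rise.

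The plausibility judgement is then hard to make. The protocol's yardsticks in Section 17 are yearly rates: the threshold of 12, more than 30 on demand, and 6.5 on FVIII prophylaxis. Δ_i is a count with no time attached.

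This is the only check of the missing-at-random assumption in Section 17, in a trial where lack of efficacy at the top dose is itself a reason for mandatory discontinuation (Section 6.4, item 9). It should be readable.

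**Working it through.** **1. Is the missing time known?** Each patient's clock starts at visit 2, trial day 1 (Section 8.1.9.1). Included data stop on a recorded date (Section 17.3), and the cut-off is one date for all (Sections 7 and 17). So

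missing main-part time = cut-off − date included data stop.

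The cut-off is set by an event, not fixed in advance, but it is known when the analysis is run. From the Section 7 milestones: last first visit 16 December 2017, plus 14 to 21 days to visit 2, plus 24 weeks gives about 16 to 23 June 2018. First treatment was 30 August 2017, so potential follow-up runs from 24 to about 42 weeks. The mean is about 33 weeks, or 33/52 × 12 = 7.6 months, in line with the 8 months in Section 17.1.

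**2. Reproducing the plan's power.** Inputs from Section 17.1: "an annual bleeding rate of 4 is assumed for the end dose concizumab regimen"; "an over-dispersion of 6 over the 24 weeks in the main part of the current trial is deemed realistic"; sufficient inference "is judged to be accommodated by 30 patients"; duration "is on average 6 months in the below calculations". The mean is 4 × 0.5 = 2 bleeds. From variance/mean = 1 + k × mean, k = (6 − 1)/2 = 2.5.

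- Closed form: Φ[ln(12/4)/√(6/(30 × 2)) − 1.96] = Φ(1.51) = 93.5%.
- Simulation with an intercept-only negative binomial fit and Wald limit: 95.7%, against about 95% stated. All nine cells of Table 17-1 reproduce within 2 points.
- Criterion 2, "on average 8 months with an average ABR of 5.4 for the concizumab treated patients": k = 5/2.7 = 1.85, mean 3.6, over-dispersion 1 + 1.85 × 3.6 = 7.67. Closed form 85.0%, simulation 88.9%, stated 87%.

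The model therefore matches the sponsor's.

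**3. One typical data set, criterion 1.** 33 dosed (Section 6.1). Thirty patients have 31 counted weeks each (33 minus run-in) and bleeds at the quantiles of the ABR 4 distribution. Three stop at week 8 with 6 counted weeks, no bleeds and 25 weeks missing. The starting point is ABR 3.64, upper limit 6.66. Add 5 bleeds to each of the three:

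- As written, they enter at 5/(6/52) = 43 per year. ABR 6.63, upper limit 12.8: tipped.
- With the 25 weeks added: ABR 4.27, upper limit 7.3: not tipped.
- The assumption itself is only 5/(25/52) = 10.4 per year over the missing time.

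**4. Simulated range.** True ABR 4, k = 2.5, potential follow-up uniform on 24 to 42 weeks, trial otherwise successful. Entries are the median tipping Δ per discontinuer, with the implied bleeds per year over the missing time in brackets. The same Δ was given to every discontinuer.

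| Discontinuers | Week | As written | Time counted |
|---|---|---|---|
| 3 | 4 | 3 (5) | 20 (36) |
| 3 | 8 | 5 (10) | 19 (39) |
| 3 | 16 | 10 (28) | 20 (60) |
| 1 | 4 | 6 (11) | 44 (87) |
| 1 | 8 | 12 (23) | 47 (100) |
| 1 | 16 | 23 (71) | 44 (152) |
| 6 | 8 | 3 (6) | 12 (26) |

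A repeat simulation gave similar rates: three at week 4, about 6 against 36; three at week 8, about 12 against 41; three at week 16, about 30 as written; one at week 16, about 73 as written. For criterion 2 (ABR 5.4, three at week 8) the tip is Δ = 5 (10 per year) as written and 17 (35 per year) with time counted.

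With three at week 8, 74% of otherwise successful trials tip as written at an implied rate of 12 per year or less, against 1% with time counted. At week 4 it is 100% against 0%.

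**The case against.** - **Criterion 1 is different.** Its offset is time on the last dose level. A discontinuer might have been escalated under Section 5.3.1, which would restart his counted time. For a patient whom the protocol requires to stop at the top dose, further time on that dose is counterfactual. This stands. A reader might infer that the sentence in Section 17.4 is wrong for both criteria, but the documents show that outright only for criterion 2. For criterion 1 the calendar time is usable only with a stated assumption of no further escalation.
- **Δ_i is indexed by patient** and could be scaled to each patient's missing time in the SAP. That is fair, and the protocol does not impose a common Δ. But scaling Δ_i does not repair an offset that omits the time in which those bleeds are supposed to occur.
- **Δ can be converted to a yearly rate afterwards.** True, so the scale is not beyond interpretation. The conversion still describes the assumption and leaves the upper limit distorted.
- **The scenarios are assumed.** This stands. A reader might take three as the planned main-part loss, because 33 are to start and 30 to complete. Section 6.1 counts completion of the whole trial. The protocol gives neither the number nor the timing of main-part discontinuations.
- **The error is conservative.** This stands too. Adding bleeds without time overstates the rate, so a result that survives is robust, and the proof-of-concept decision rests on the confidence interval and not on this analysis. It would be wrong to infer that the plan could produce a false efficacy claim.

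**Conclusion.** The point holds in limited form and should be corrected. The stated reason for freezing the offset is incorrect for criterion 2, and for criterion 1 it can be replaced by one explicit assumption.

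The size depends on how early and how many patients leave. Three early drop-outs (weeks 4 to 8) tip the result at about 5 to 12 bleeds per year over the missing time, around or below the threshold of 12; with the time counted it takes about 36 to 41, above the on-demand level the protocol cites. With three at week 16 the contrast is about 28 to 30 against 60, and with one at week 16 about 71 to 73 against about 150. It does not follow that the planned analysis always tips at mild assumptions. Nor does counting the time always give reassurance: with six at week 8 the tip is about 26 per year.

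The damage is to interpretation only. A result that survives the planned analysis can be trusted, but one that tips early cannot be called fragile. These figures rest on ABR 4, over-dispersion 6, 33 dosed, uniform potential follow-up and the assumed drop-out patterns.

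**What to change.** In Section 17.4:

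1. Delete the sentence saying that the missing time cannot be identified.
2. For each discontinuer, define missing time as the cut-off minus the date his included data stop, and add it to the offset.
3. Set Δ_i as an assumed bleeding rate times that missing time. Direct addition is enough; multiple imputation at an assumed rate is one option.
4. Raise the rate until the upper limit reaches 12, and report the tipping point in bleeds per year beside the yardsticks of 12 and more than 30.
5. Do this for each criterion with its own data and offset from Section 17.3. For criterion 1, state the assumption that the patient would have stayed on the last dose level reached.

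The cost is a change of wording in the protocol or SAP and a little programming. No new data are needed, because the dates are already collected.

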17.5 Additional analyses

An additional evaluation of the primary endpoint will be made, including actual concizumab dose level (interpreted as the patient's last dose level) as *additional factor in the primary analysis model specified above*. Point estimates and 95% confidence interval will be provided for the ABR at the different dose levels of concizumab (0.15, 0.20 and 0.25 mg/kg). Furthermore, a series of analyses with individual steady state PK/PD assessments included as covariates in the negative binomial regression model as specified for the primary analysis will be performed in order to evaluate possible associations between PK/PD and ABR that potentially could guide dose-selection. The referred steady-state PK/PD assessments comprise the concizumab trough level, maximum plasma concentration (C_{max}) of concizumab, TFPI value prior to the last s.c. dose administration, peak thrombin generation (nM), Endogenous thrombin potential (nM*min) and velocity index (nM/min).

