Daily dosing with 0.15 mg/kg aims to ensure steady-state levels of concizumab plasma concentrations above 100 ng/mL for the majority of the patients starting on this dose. The PK results from explorer^{TM3} showed exposure-response in terms of fewer bleeding episodes recorded for patients who reached plasma concentrations of concizumab above 100 ng/mL see [Figure 3-1](#). The minority of patients which are predicted to have steady-state plasma concentrations below this threshold are expected to experience bleeding episodes and therefore will have the opportunity to be dose-escalated to the dose of 0.2 mg/kg. A further dose escalation to 0.25 mg/kg per day is permitted, again based on the bleeding rate, see section [5.3.1](#).

Protocol
 Trial ID:NN7415-4255
 UTN:U1111-1179-3872
 EudraCT no.:2016-000614-29

~~CONFIDENTIAL~~

Date: 28 August 2018
 Version: 5.0
 Status: Final
 Page: 32 of 127

Novo Nordisk

Figure 5–2 Individual predicted concizumab concentration profiles for all concizumab-treated patients in explorerTM2 (n=4 patients) and explorerTM3 (n=18 patients). The horizontal lines indicate 100 ng/mL, and the shaded areas represent the full range (min-max) of the individual predicted profiles¹.

Due to the high between-patient variability in concizumab concentration observed in explorerTM3, a significant overlap in plasma concentrations of concizumab in patients who received 0.25, 0.5 and 0.8 mg/kg doses was seen, see [Figure 5–2](#). Therefore, choosing three doses that would lead to reasonably distinct mean plasma concentrations of concizumab, and thus different efficacy at each dose level was not deemed possible. For this reason, a traditional parallel arm design was not chosen for the phase 2 trials. In contrast, the titration trial design allows patients to start on a low dose, which is expected to ensure prophylaxis but not marked changes in coagulation parameters, for the majority of patients. Escalation to the next dose level will only occur in the case of lack of efficacy (≥ 3 spontaneous bleeding episodes within the preceding 12 weeks). In addition, the PK of concizumab is heavily influenced by target mediated drug disposition, which means that small differences in concizumab dose ultimately leads to large differences in plasma concentrations. Therefore, daily dosing is proposed for the phase 2 trial, explorerTM5. Daily dosing will allow for the increase in trough levels and thus better efficacy may be expected with a lower dose.

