Embryonic exposure in pregnant female partners of men treated with concizumab is highly unlikely and there is no need for protocol requirements for use of contraception in phase 2 and 3 trials.

¹ Plasma concentrations in the same range as those in explorerTM3 are expected to be reached in this trial with daily dose administration. The starting dose for all patients will be 0.15 mg/kg daily. The plasma steady-state exposure for a typical subject at this dose level is predicted to fourfold lower compared to a typical subject on 0.8 mg/kg Q4D (cohort 3 of explorerTM3) in terms of both C_{max} and AUC 0-24h. For 0.20 mg/kg daily and 0.25 mg/kg, the plasma steady-state exposure levels for a typical subject are predicted to be less than 40% and 70% respectively, compared to the typical subject exposure in the 3rd cohort of explorerTM3 (AUC and C_{max}). The maximum predicted plasma exposure levels (C_{max} and AUC 0-24h) for the 0.15 mg/kg daily dose level is predicted to be more than 8 fold lower than for 0.80 mg/kg Q4D. For 0.20 mg/kg daily both C_{max} and AUC 0-24h are predicted to be more than 3 times lower than for 0.80 mg/kg Q4D. For 0.25 mg/kg daily, the maximum C_{max} and AUC 0-24h are predicted to be 35 % lower than for 0.80 mg/kg Q4D.

Protocol
 Trial ID: NN7415-4255
 UTN: U1111-1179-3872
 EudraCT no.: 2016-000614-29

~~CONFIDENTIAL~~

Date: 28 August 2018
 Version: 5.0
 Status: Final
 Page: 33 of 127

Novo Nordisk

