5.3.1 Dose escalation

Bleeding episodes will be assessed during the trial both at scheduled visits and also between visits. The first 2 weeks of the treatment with concizumab 0.15 mg/kg is considered as a run-in period. Hence the bleeding episodes occurring during the first 2 weeks should not influence a dose escalation decision.

All spontaneous bleeding episodes (sBEs) are counted from 2 weeks after visit 2 (first-dose visit) until visit 16 (end-of-treatment visit), i.e. a total of up to 124 weeks. Dose-escalation will be based on the number of spontaneous, treated bleeding episodes in patients within preceding 12 weeks. However, before dose-escalation can occur, to ensure the safety of the patients, the investigator must take into account the full clinical picture the patient is presenting with and all available laboratory results, including coagulation parameters.

Dose 0.15 mg/kg:

When a sBE occurs, the investigator will determine if ≥ 3 sBEs have occurred within the preceding 12 weeks since visit 2+2weeks (including the current sBE). If yes, and if investigator deems it safe, the patient will have to be dose escalated from 0.15 to 0.20 mg/kg at the next scheduled visit. If the investigator judges that this visit is scheduled too late, he/she should contact the patient for an unscheduled visit.

Dose 0.20 mg/kg:

When an sBE occurs, the investigator will determine if ≥ 3 sBEs have occurred within the preceding 12 weeks (including the current sBE), counting only new sBEs from the beginning of the 0.20 mg/kg treatment period. If yes, and if investigator deems it safe, the patient will have to be dose escalated from 0.20 to 0.25 mg/kg at the next scheduled visit. If the investigator judges that this visit is scheduled too late, he/she should contact the patient for an unscheduled visit.

Dose 0.25 mg/kg:

Patients are not dose escalated further regardless of the number of sBEs. When an sBE occurs, the investigator will determine if ≥ 3 sBEs have occurred within the preceding 12 weeks (including the current sBE), counting only the new sBEs from the beginning of the 0,25mg/kg treatment period. If yes, then the patient must be discontinued from treatment due to lack of efficacy, see Section [6.4](#).

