17.8 Interim analysis

The trial does not include a formal interim analysis. However, the split of the trial into a main and extension part offers the opportunity of reporting results before the end of the trial. Other reporting of the trial might be done during the extension part once the data collection and review of the main part data has been finalised and individual clinical study reports might in such case be issued. A final clinical study report describing results from the main and extension part will be written when the last patient has either completed or withdrawn from the trial.

All main conclusions regarding clinical proof of concept and dose guidance for phase 3 will be based on the reporting after the main part, see [Figure 17-1](#).

[figure not shown]

Figure 17-1 Definition of main and extension part

Protocol
 Trial ID:NN7415-4255
 UTN:U1111-1179-3872
 EudraCT no.:2016-000614-29

~~CONFIDENTIAL~~

Date: 28 August 2018
 Version: 5.0
 Status: Final
 Page: 110 of 127

Novo Nordisk

18 Ethics

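### Section 17.5 groups patients by last dose reached, which their bleeding decides, so its estimates are not the ABR at each dose level

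*Protocol*

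**What the plan says.** Section 17.5 plans a further evaluation of the primary endpoint, "including actual concizumab dose level (interpreted as the patient's last dose level"), as an added factor in the primary negative binomial model. Its output is described as follows: "Point estimates and 95% confidence interval will be provided for the ABR at the different dose levels of concizumab (0.15, 0.20 and 0.25 mg/kg"). Protocol Amendment 3 added the definition as last dose level, so it is a deliberate specification.

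Dose is not randomised. Section 5.2: "The starting dose for all patients will be 0.15 mg/kg daily". Also Section 5.2: "Escalation to the next dose level will only occur in the case of lack of efficacy". Section 5.3.1: "Dose-escalation will be based on the number of spontaneous, treated bleeding episodes in patients within preceding 12 weeks". The trigger is three or more such bleeds. At 0.25 mg/kg, "Patients are not dose escalated further regardless of the number of sBEs"; a patient who meets the same bleed count there leaves treatment (Sections 5.3.1 and 6.4).

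Section 17.8: "All main conclusions regarding clinical proof of concept and dose guidance for phase 3 will be based on the reporting after the main part".

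**The concern.** Treated spontaneous bleeds are a subset of the primary endpoint. A factor set by counting them is an outcome, not an exposure. Under this definition the 0.15 mg/kg row holds patients who did not bleed enough to escalate, the 0.20 row those who failed once, and the 0.25 row those who failed twice. The model has no term that separates dose from a patient's own tendency to bleed.

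What escalators experienced at 0.15 mg/kg is lost to that row under either data rule. With first-criterion data it is dropped; with all main-part data it is charged to the higher dose.

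A reader of a table headed as ABR at each dose level would compare the rows. The comparison would very likely favour the lowest dose whatever the true dose effect, and the 0.15 figure would be too low in absolute terms. Section 17 cautions about possible bias in the first proof-of-concept criterion because data are discarded. No caution accompanies the by-dose estimates.

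**Working it through.** **Inputs from the protocol.** ABR 4 at end dose and 5.4 including pre-escalation data; over-dispersion 6; 30 patients for power; 6 months' average exposure for the first criterion; threshold 12 (Sections 17 and 17.1). 33 patients dosed (Section 6.1). Escalation rule, bleed count restarting at each dose, and first 2 weeks ignored (Section 5.3.1).

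**Assumptions not in the protocol.** 70% of bleeds spontaneous (range 50 to 90%). Main-part follow-up uniform over 24 to 41 weeks, that is 24 weeks plus up to about 17 weeks for the four-month recruitment in Section 7. Escalation at the next 4-weekly visit. Gamma-distributed patient rates. 5.4 taken as the true ABR at 0.15 mg/kg. One common rate ratio per dose.

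**Step 1: reproduce the plan's power.** Read over-dispersion as variance/mean. Mean = 4 × 0.5 = 2. SE of log ABR = √(6/(30 × 2)) = 0.316. Power = Φ(ln(12/4)/0.316 − 1.96) = Φ(1.51) = 93.5%. Simulated negative binomial fits give 96.0%. The plan states about 95%, so this reading of over-dispersion is supported. By simulation, seven of the nine cells of Table 17-1 agree within 2 points; the other two differ by 2.4 and 2.1.

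**Step 2: spread between patients.** Variance/mean = 1 + mean/shape, so shape = (5.4 × 0.5)/(6 − 1) = 0.54.

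**Step 3: apply the escalation rule and tabulate ABR by last dose (last-dose period only).**

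| True ABR at 0.15 / 0.20 / 0.25 | Table would show |
|---|---|
| 5.4 / 5.4 / 5.4 (no dose effect) | 2.3 / 8.1 / 20.4 |
| 5.4 / 3.8 / 2.7 (30% and 50% lower) | 2.3 / 6.6 / 12.0 |
| 5.4 / 2.2 / 1.1 (60% and 80% lower) | 2.3 / 4.5 / 6.0 |

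With no dose effect, spontaneous shares of 50 to 90% give 1.8–3.0 / 6.1–11.2 / 17.5–25.0. Independent repeat simulations gave 2.2 / 8.3 / 19.2 to 20.4 at ABR 5.4, and 1.7 / 8.1 / 19.9 at ABR 4. Charging the whole main part to the last dose gives 2.3 / 11.1 / 22.7.

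Selection is the cause. With no dose effect, patients ending at 0.15, 0.20 and 0.25 have mean personal rates of 2.7, 10.4 and 21.4 per year.

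**Step 4: trials of 33 patients** (median 7 escalate). The escalated group shows the higher ABR in 99.5% of trials with no dose effect, 98.5% with 30%/50% benefit and 92% with 60%/80% benefit.

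**Step 5: candidate repairs on the same simulated data.**

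| Method | No effect (truth 1, 1) | Truth 0.7, 0.5 | Truth 0.4, 0.2 |
|---|---|---|---|
| Fixed-effect within-patient rate ratios | 0.80, 0.76 | 0.55, 0.36 | 0.31, 0.14 |
| Joint likelihood, time-varying dose, shared patient random effect | 1.01, 1.00 | 0.70, 0.49 | 0.40, 0.21 |

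Plain person-time by dose taken gives ABRs of 4.0 / 14.0 / 20.5 when the truth is 5.4 throughout, so relabelling alone does not help. The fixed-effect contrast errs the other way because the bleeds that trigger escalation are counted at the lower dose.

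**Step 6: a steep-response alternative.** Section 17 expects patients on an ineffective dose to bleed as if untreated. Assume 70/20/10% of patients are first protected at 0.15/0.20/0.25, with ABR 3 if protected and 30 if not. The population rates are then 0.7 × 3 + 0.3 × 30 = 11.1; 0.9 × 3 + 0.1 × 30 = 5.7; and 3.0. The last-dose table shows 2.9 / 3.6 / 3.5. Varying heterogeneity gave 3.0 / 3.4 / 3.2 to 2.0 / 3.2 / 4.5. Under this model the random-effect model also misses: 0.35 and 0.09, against true ratios of 5.7/11.1 = 0.51 and 3.0/11.1 = 0.27.

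**The case against.** The strongest reply is that this is one additional analysis, outside the two-criterion hierarchy, with no test and no promised contrast or trend between doses. The last-dose definition is stated openly. Section 5.2 explains that titration was chosen because doses with clearly separate exposure and efficacy could not be found, and Section 17 argues that last-dose data show what the drug does in that particular patient. ABR among patients who end on a dose is a fair description of a titration regimen.

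Much of this stands. It supports a table described as ABR by last dose reached. It does not support calling the rows ABR at the dose levels, because efficacy within a given patient says nothing about comparing different patients across doses.

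The size of the gradient also depends on the response model. Under steep response it largely flattens, so the large rise is not inevitable. The 0.15 row is still badly wrong there: 2.9 against 11.1.

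A reader might infer that the protocol makes this table the basis for choosing the phase 3 dose. It does not. The remark in Section 17.5 about guiding dose selection belongs to the separate PK/PD covariate series. The link for the by-dose ABRs runs only through the general sentence in Section 17.8, which covers the whole main-part report.

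**Conclusion.** The point holds for the by-dose estimates. Section 17.5 fixes a factor that bleeding determines and labels the output as ABR by dose level. At the planned ABR of 5.4 and over-dispersion 6, under the assumptions above, the table would show about 2 / 8 / 20 with no dose effect and about 2.3 / 6.6 / 12 under a true 30%/50% benefit. It will very likely make the higher doses look worse: 92 to 99.5% of simulated trials under a common rate ratio. It understates the 0.15 mg/kg rate under both response models tried.

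Two stronger readings are not supported. The proof-of-concept decision is untouched, since neither criterion in Section 17 uses dose as a factor. Nor is a reversed dose-response certain: the magnitudes rest on the assumed spontaneous share, follow-up and form of response, and a steep response shrinks the gradient. The defect itself does not wait on the SAP, because the protocol states the rule.

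**What to change.** In Section 17.5, replace last dose level by the dose being taken. Split all main-part data by dose period and fit by joint likelihood a negative binomial (Poisson-gamma) model with dose period as a time-varying factor, log period exposure as offset and a shared patient random effect. Say explicitly that neither plain person-time relabelling nor a fixed-effect within-patient contrast is meant, since both stay biased. State the assumption of a common rate ratio per dose, because the model is not reliable if response is a threshold.

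If the last-dose table is kept, title it *ABR by last dose reached (descriptive)* and state that it is not a dose-response and will not be used for phase 3 dose guidance.

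Cost: protocol wording and slightly more programming. Doses, dates and bleeds are already collected. The price is dependence on the model and wide intervals at 0.20 and 0.25 mg/kg, with a median of about 7 escalators among 33 patients in the simulations.
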